#### **Study Design/Methods:**

Participants who have signed an EC/IRB-approved informed consent form and have met all the protocol eligibility criteria during screening may be enrolled into the study in a double-blind or open label fashion depending on the cohort. Cohorts 1 through 4 (NHVs) will begin with administration of ARO-HSD or PBO to two sentinel participants (one ARO-HSD, one PBO). Following the Day 3 evaluation in these participants, if there are no significant safety concerns, the remaining participants in the cohort will be treated at the discretion of the Principal Investigator (PI). Dosing of participants will be staggered by at least 30 minutes such that no two participants will be dosed simultaneously. Sentinel dosing is not required in NASH/suspected NASH patient cohorts.

[figure not shown]
Dose levels by cohort are outlined in the Cohort Summary above and Dose Escalation Schedule below. NHV Cohorts 1 through 4 will enroll sequentially with patient cohorts opening for enrollment in a step-wise manner. Screening for all cohorts may begin once Cohort 1 has been opened for enrollment.

Dose escalation will require approval by the DSC based on all cumulative available safety data for prior cohorts, and through at least Day 15 of the current cohort as shown in Figure 1. Based on this cumulative safety data the DSC will vote to approve dose escalation to the next single dose NHV cohort as well as vote to open a NASH/suspected NASH patient cohort at the dose most recently tested in NHVs. Escalation to the next dose level will proceed until the highest planned dose level is completed, or the trial is halted prematurely by the PI, DSC, or Sponsor due to safety or other reasons. Where specified, dose levels represent the highest dose which may be used. The DSC may adjust doses downward if indicated based on review of available safety data and pharmacodynamic data (if available). All subjects who withdraw from the study prior to their End of Study (EOS) visit, for reasons other than an AE, may be replaced.

Cohort 1b (25 mg on Days 1 and 29) will enroll sequentially after Cohorts 3b and 4b are enrolled and will not require DSC approval to initiate enrollment as the dose is lower than the 200 mg top dose used in cohorts 4 and 4b which have already been opened by the DSC.

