## Treatment Stopping Rules:

Escalation to the next cohort will proceed according to the study design until the highest planned dose cohort is completed, unless the trial is stopped early by the DSC, PI or Sponsor. A decision to stop the trial early or discontinue drug in an individual subject, group of subjects or to halt enrollment temporarily or permanently may be indicated based on any of the following:

- 1. A serious adverse reaction (i.e., a serious AE [SAE] considered at least possibly related to the IMP administration) in ONE subject; or severe non-serious adverse reactions (i.e. severe non-serious AEs considered as, at least, possibly related to the IMP administration) in TWO subjects in the same cohort, independent of whether or not the events occur within the same system-organ-class.
- 2. One of the following abnormal results at least possibly related to ARO-HSD:
- In NHV cohorts:
  - Treatment emergent AST and/or ALT > 8X ULN which must be confirmed by repeat blood draw within 48 hours of initial results; OR
  - A treatment emergent AST or ALT >3X ULN (must be confirmed on repeat) with a total bilirubin >2X ULN (must be confirmed on repeat); OR
  - o A treatment emergent ALT or AST >3X ULN (must be confirmed on repeat) with symptoms of RUQ pain, fever, rash or eosinophilia; OR
  - A treatment emergent AST or ALT >3X ULN (must be confirmed on repeat) with an INR > 1.5 (must be confirmed on repeat) and which must not be explained by another plausible cause
- See Appendix 16.1 for treatment modification guidelines in subjects/patients (NASH/Suspected NASH patients) with baseline/pre-dose elevated ALT or AST.

If such serious adverse reactions or severe non-serious adverse reactions occur, enrollment and dosing in healthy volunteers will be paused pending a review of safety data and a decision on how to proceed by the DSC.

Sponsor or PI can discontinue any subject at any time with or without DSC consultation. If such events (as described in #1, #2 above) occur and the subject is not discontinued from the study, the reason for not discontinuing the subject will be included in DSC meeting minutes. Including, but not limited to the events listed above, the DSC may pause the study to additional dosing or dose escalation to provide time to evaluate safety data and recommend the action to be taken, which may include, but is not limited to, one of the following:

- Discontinuation of a subject or group of subjects from the study

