target silencing with less frequent dosing (Cohort 3c). However, Cohort 3c (ARO-HSD 100 mg on Days 1 and 85) is removed from protocol version 7.0 as the enrolled NHV cohorts as well as the three patient cohorts (3b, 4b and 1b) will provide sufficient preliminary data informing on safety, tolerability, pharmacodynamics, pharmacokinetics as well as dose response of multiple dose ARO-HSD necessary for future Phase 2 study planning.

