#### 7. STUDY PLAN

## 7.1 Study Design

Participants who have signed an EC/IRB approved informed consent form and have met all the protocol eligibility criteria during screening may be enrolled into the study in a double-blind or open label fashion depending on the cohort. Cohorts 1 through 4 will begin with administration

of ARO-HSD or PBO to two sentinel participants (one ARO-HSD, one PBO). Following the Day 3 evaluation in these participants, if there are no significant safety concerns, the remaining participants in the cohort will be treated at the discretion of the Principal Investigator (PI). Dosing of participants will be staggered by at least 30 minutes such that no two participants will be dosed simultaneously. Sentinel dosing is not required in patient cohorts.

Dose levels by cohort are outlined in Table 4 and Figure 1. Cohorts 1 through 4 will enroll sequentially with patient cohorts opening for enrollment in a step-wise manner. Screening for all Cohorts may begin once Cohort 1 has been opened for enrollment.

Clinical facility confinement will be approximately 3 days for first dose administration in NHV cohorts (Cohorts 1, 2, 3, and 4) with discharge on Day 2. Subjects will return to the clinical facility for outpatient visits per the Schedule of Assessments. Subjects in cohorts 1b, 3b and 4b will be at the facility for approximately 4 hours (2 hours before dosing and 2 hours after dosing) on dosing days.

**Table 4** Cohort Summary

		T	I	
Cohort	Population	Blinding	# Subjects	Dosing Schedule
1	NHVs	Double blind	8 (4 active:	25 mg Day 1 only
			4 placebo)	
1b	Patients with suspected NASH	Open Label	up to 6	25 mg Days 1, 29
	(biopsies on screen and day 71)		(all active)	
2	NHVs	Double blind	8 (4 active:	50 mg Day 1 only
			4 placebo)	
3	NHVs	Double blind	8 (4 active:	$\leq 100 \text{ mg Day 1 only}$
			4 placebo)	
4	NHVs	Double blind	8 (4 active:	$\leq$ 200 mg Day 1 only
			4 placebo)	
3b	Patients with suspected NASH	Open Label	up to 6	$\leq$ 100 mg Days 1, 29
	(biopsies on screen and day 71)		(all active)	
4b	Patients with suspected NASH	Open Label	up to 6	≤ 200 mg Days 1, 29
	(biopsies on screen and day 71)		(all active)	

[figure not shown]

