In the NHV and suspected NASH patient dose escalation part of the study, dose escalation will require approval by the DSC based on all cumulative available safety data for prior cohorts, and through at least Day 15 of the current cohort. Based on available safety data through Day 15, the DSC will vote to approve dose escalation to the next single dose NHV cohort as well as vote to open a suspected NASH patient cohort at the dose most recently tested in NHVs. DSC decisions will be based on all aggregate safety data available including all data available at least through Day 15 of the current cohort as shown in Figure 1. Escalation to the next dose level will proceed until the highest planned dose level is completed, or the trial is halted prematurely by the PI, DSC, or Sponsor due to safety or other reasons. All subjects who withdraw from the study prior to their EOS visit, for reasons other than an adverse event, may be replaced.

Cohort 1b will enroll after completion of cohorts 3b and 4b and will not require DSC approval to initiate enrollment as they use doses lower than the 200 mg top dose used in cohorts 4 and 4b which have already been opened by the DSC.

In double-blind cohorts, treatment un-blinding may occur at the PI's discretion only where deemed necessary for treatment of an AE or for a decision to be made regarding trial continuation. After all subjects in a cohort have completed the final planned study visit (not including the 90-day follow-up call), Sponsor may be unblinded at Sponsor's request. After all subjects in double blinded cohorts have completed their EOS visit (not including the 90-day follow-up call), all blinded cohorts may be unblinded.

Single and multiple doses of ARO-HSD will be evaluated in in a sequential manner as shown in Figure 1.

Figure 1: Dose Escalation Schedule

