## 7.4 **Stopping Rules**

A decision to stop the trial early or discontinue drug in an individual subject, group of subjects or to halt enrollment temporarily or permanently may be indicated based on any of the following:

- 1. A serious adverse reaction (i.e. an SAE considered at least possibly related to the IMP administration) in ONE subject; or severe non-serious adverse reactions (i.e. severe non-SAEs considered as, at least, possibly related to the IMP administration) in TWO subjects in the same cohort, independent of whether or not the events occur within the same system-organ-class.
- 2. One of the following abnormal results at least possibly related to ARO-HSD:
  - In NHV cohorts:
    - o Treatment emergent AST and/or ALT > 8X ULN which must be confirmed by repeat blood draw within 48 hours of initial results, OR

- A treatment emergent AST or ALT >3X ULN (must be confirmed on repeat) with a total bilirubin >2X ULN (must be confirmed on repeat), OR
- A treatment emergent ALT or AST >3X ULN (must be confirmed on repeat) with symptoms of RUQ pain, fever, rash or eosinophilia, OR
- A treatment emergent AST or ALT >3X ULN (must be confirmed on repeat) with an INR > 1.5 (must be confirmed on repeat) and which must not be explained by another plausible cause
- See Appendix 16.1 for treatment modification guidelines in patients with baseline/pre-dose elevated ALT or AST.

If such serious adverse reactions or severe non-serious adverse reactions occur as outlined above, enrollment and dosing in healthy volunteers will be paused pending a review of safety data and a decision on how to proceed by the DSC.

The Sponsor or PI can discontinue any patient at any time with or without DSC consultation. If such events (as described above) occur and the patient is not discontinued from the study, the reason for not discontinuing the patient will be included in DSC meeting minutes. Including, but not limited to the events listed above, the DSC may pause the study to additional dosing or dose escalation to provide time to evaluate safety data and recommend the action to be taken, which may include, but is not limited to, one of the following:

- 1. Discontinuation of a patient or group of patients from the study.
- 2. The study is stopped immediately with no further dosing
- 3. The study will continue until the current cohort is completed.

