#### 13.4 Written Informed Consent

Informed consent will be obtained before the patient can participate in the study. The contents and process of obtaining informed consent will be in accordance with all applicable regulatory requirements. Study participation includes all screening procedures, as well as any wash-out of excluded medications.

It is the responsibility of the PI (or medically qualified designee) to obtain a written informed consent from everyone participating in this study after adequate explanation of the aims, methods, objectives, and potential hazards of the study. The PI (or medically qualified designee) must also explain to the participants that they are completely free to refuse to enter the study or to withdraw from it at any time. Appropriate forms for documenting a written consent will be provided by the PI or by Arrowhead Pharmaceuticals, Inc.

For this study, each eligible participant will be required to provide written informed consent before participation in the study.

All eligible participants will have the study explained by the PI or designee. They will receive a full explanation, in lay terms, of the aims of the study, the discomforts, risks and benefits in taking part as well as of insurance and other procedures for compensation in case of injury. It will be explained that the study is for research purposes only and is not expected to provide any therapeutic benefit to the individual. It will be pointed out that they can withdraw from the study at any time without prejudice. Each participant will acknowledge receipt of this information by giving written informed consent for participation in the study. The volunteer will be given a copy of the signed Informed Consent Form to retain.

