# 15. INFORMATION DISCLOSURE AND INVENTIONS

# 15.1 Ownership

# 15.2 Confidentiality

#### 15.3 **Publication**

# 16. APPENDICES

# 16.1 Study Modification Guidelines For Subjects And Patients With Baseline Pre-Dose Evidence Of Liver Disease

Treatment-Emergent ALT	Treatment-Emergent Total Bilirubin (TBL)	Liver Symptoms	Action
Normal baseline with treatment emergent (TE) increase to ALT > 5x ULN  Elevated baseline with TE increase to: ALT > 3x baseline or > 300 U/L (whichever occurs first)	Normal	None	Repeat ALT, AST, ALP, TBL, in 2–3 days Follow-up for symptoms.
Normal baseline with TE increase to ALT > 8x ULN  Elevated baseline with TE increase to: ALT > 5x baseline or > 500 U/L (whichever occurs first)	Normal	None	Interrupt study drug. Initiate close observation and workup for competing etiologies. (see below)  Study drug can be restarted only if an alternative etiology is identified and liver enzymes return to baseline.
Normal baseline with TE increase to ALT > 3x ULN  Elevated baseline with TE increase to ALT > 2x baseline or > 200 U/L (whichever occurs first)	TBL > 2x ULN	None	Interrupt study drug. Initiate close observation and workup for competing etiologies.  Study drug can be restarted only if an alternative etiology is identified and liver enzymes return to baseline.

Normal baseline with	Normal or elevated	Symptoms of	Interrupt study drug.
TE increase to ALT		clinical	Initiate close observation
> 3x ULN		hepatitis -	and workup for
		severe fatigue,	competing etiologies.
Elevated baseline with		nausea,	
TE increase to ALT >		vomiting,	Study drug should not
2x baseline or $> 200$		right upper	be restarted
U/L		quadrant	
(whichever occurs first)		pain	

Source: Adapted from Chalasani, Naga and Regev, Arie et al. Drug-Induced Liver Injury in Subjects with Preexisting Chronic Liver Disease in Drug Development: How to Identify and Manage? Gastroenterology, Volume 151. Issue 6, 1046 – 1051

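### If a related serious reaction occurs in Cohort 3b or 4b, the automatic pause covers healthy volunteers only: nothing automatically holds patient dosing or the opening of Cohort 1b until the DSC has reviewed it

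*Protocol*

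**What the plan says.** Protocol 7.4 and the synopsis stopping rules list two criteria. Criterion 1 is a serious reaction at least possibly related to study drug in one subject, or related severe non-serious reactions in two subjects of one cohort. It is not limited by population. Criterion 2 lists liver thresholds for the healthy-volunteer cohorts and sends patients with raised baseline enzymes to Appendix 16.1.

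When serious or severe reactions of the criterion 1 kind occur, 7.4 says that "enrollment and dosing in healthy volunteers will be paused pending a review of safety data and a decision on how to proceed by the DSC". In the synopsis the restriction is the same: "enrollment and dosing in healthy volunteers will be paused pending a review of safety data". Everything else in the rule is discretionary. A halt *may* be indicated, the DSC *may* pause the study, and the sponsor or investigator *can* discontinue a subject.

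On Cohort 1b, Protocol 7.1 says: "Cohort 1b will enroll after completion of cohorts 3b and 4b and will not require DSC approval to initiate enrollment". The synopsis says that it "will enroll sequentially after Cohorts 3b and 4b are enrolled and will not require DSC approval to initiate enrollment". The reason given in both places is that the dose is below the 200 mg already opened by the DSC.

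Protocol 5.6 describes the state of the trial at this version: "the enrolled NHV cohorts as well as the three patient cohorts (3b, 4b and 1b) will provide sufficient preliminary data". Protocol 7.1 adds: "Sentinel dosing is not required in patient cohorts".

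**The concern.** The trigger covers everyone, but the automatic response covers only volunteers. Volunteers receive one dose each, and at this version their cohorts are described as enrolled, so apart from replacements that pause has little planned dosing left to act on. Cohorts 3b, 4b and 1b are the only two-dose groups, and they are where the remaining planned dosing lies.

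The Cohort 1b waiver makes sense if 3b and 4b have been uneventful, but it has no exception for when they have not. The stake is that a patient could receive a first or second dose after a related serious reaction in another patient and before the DSC has considered it, with the protocol fully complied with. Patients do not have sentinels, and Protocol 13.4 has participants told that the study is "not expected to provide any therapeutic benefit to the individual". On the face of the documents, then, expected benefit is not a reason to keep dosing patients while volunteers are paused.

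**Working it through.** **1. Cohort sizes.** From the cohort table in Protocol 7.1: volunteers 4 cohorts x 8 = 32; patients 3 cohorts x 6 = 18; total 32 + 18 = 50. This reproduces the approximate total of 50 in Protocol 8.1.

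**2. Who can trigger criterion 1.** It speaks of one subject, or of two subjects in the same cohort. Criterion 2 is expressly restricted to the volunteer cohorts and criterion 1 is not, so an event in 3b or 4b counts. If the pause sentence were instead read as applying only to events in volunteers, a patient event would have no automatic consequence at all, and the gap would remain.

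**3. What follows, provision by provision.**

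| Provision | Force | Automatically holds patient dosing or Cohort 1b? |
|---|---|---|
| Pause sentence, 7.4 and synopsis | Mandatory | No; names healthy volunteers |
| Halt of enrolment, 7.4 lead-in | Discretionary | No |
| DSC pause of the study, 7.4 | Discretionary | No |
| DSC approval, 7.1 and 7.3 | Mandatory for dose escalation; 7.1 also has the DSC vote to open a patient cohort | No; Cohort 1b is exempted |
| DSC minutes, 7.4 | Mandatory if the subject is not discontinued | No; records the reason for that subject |
| Appendix 16.1: "Interrupt study drug. Initiate close observation and workup for competing etiologies" | Directive | No; acts on the affected patient, for liver signals |
| SAP 7.1, DSC review of accumulating data | General statement | No; gives no trigger or timing |

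The pause sentence might be parsed as all enrolment plus volunteer dosing, but the plain reading limits both nouns to volunteers.

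**4. Doses affected.** Cohort 1b: 6 patients x 2 doses = 12. The synopsis allows up to two additional patients already in screening, so at most (6 + 2) x 2 = 16. To these add any 3b and 4b doses not yet given at the time of the event. That number depends on timing and cannot be fixed from the documents.

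The start condition for Cohort 1b matters here. If completion of 3b and 4b governs (7.1), their dosing is over before 1b starts. If it is enough that they are enrolled (synopsis), some of their doses may still be due when 1b opens.

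**5. How often the situation might arise.** The documents give no event rate. As an assumption only, let p be the per-patient risk of a related serious reaction, and take the 6 + 6 = 12 planned patients in 3b and 4b. The chance of at least one event is 1 - (1 - p)^12:

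- p = 1%: 1 - 0.99^12 = 11.4%
- p = 2%: 1 - 0.98^12 = 21.5%
- p = 5%: 1 - 0.95^12 = 46.0%

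This is the chance that the trigger occurs, not the chance that patients are then dosed without review.

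**The case against.** The strongest reply is that Cohort 1b would not open in ignorance of the event. Criterion 1 covers patients and contemplates halting enrolment. Protocol 7.3 puts the sponsor's medical monitor, its head of pharmacovigilance, the investigator and an independent physician on the DSC. Serious events are reported within 24 hours. The pause sentence ends in a DSC decision, and the options listed after it are study-wide. All of this stands. A reader might infer from the waiver and the volunteer-only wording that nothing can stop Cohort 1b, or that it would open unexamined; the documents do not support that. They leave the interim hold to discretion for patients while making it automatic for volunteers on the same trigger.

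Two other inferences should be resisted:

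- **The share of all doses outside the pause.** Patient doses are 3 x 6 x 2 = 36 and active volunteer doses 4 x 4 = 16, so 36 of 52 (69%) lie outside it. That counts every 3b and 4b dose, including those already given, and credits volunteers with a protection that is largely spent. It does not measure the Cohort 1b gap.
- **Cohort 1 against Cohort 1b.** One 25 mg dose is under the automatic pause and two are not, which looks inconsistent. But Cohort 1 was the first human exposure, whereas Cohort 1b follows single doses up to 200 mg in volunteers and the higher-dose patient cohorts. Accumulated exposure could justify different handling.

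Figure 1, the dose escalation schedule, is not shown in the text available. It could carry a rule, and its absence here is not a fault in the plan.

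**Conclusion.** The point holds in a limited form. If criterion 1 is met in Cohort 3b or 4b, the visible text does not automatically hold further patient dosing, or the opening of Cohort 1b, until the DSC has reviewed the event. Twelve planned Cohort 1b doses are affected, up to 16, plus any 3b and 4b doses outstanding.

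The residual risk is limited. Cohort 1b receives 25 mg, one-eighth of the top dose (25/200), and the people able to stop dosing would know of the event. The 11% to 46% range above rests wholly on assumed rates, and a reader should not take it as the chance of harm.

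The conclusion assumes that Figure 1 contains no hold, that the pause sentence is read in its plain sense, and that Cohort 1b doses are still to be given, as the future tense in 7.1 and the synopsis indicates. This is a cheap improvement, not a defect that undermines the trial.

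**What to change.** 1. In Protocol 7.4 and the synopsis stopping rules, change *in healthy volunteers* to *in all cohorts* in the pause sentence.
2. In Protocol 7.1 and the synopsis study design, state that Cohort 1b does not open while such a pause is in force. Keep the approval waiver otherwise, with no added routine review.
3. State that isolated liver results in patients remain under Appendix 16.1.
4. Allow the DSC to extend the Day 29 dosing window (plus or minus 2 days) and the 60-day screening window for patients caught by a pause.

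The fourth item is needed because a pause could otherwise push a patient past the second dose, or past the screening period that contains the baseline biopsy.

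The cost is a short amendment, with no delay unless criterion 1 is met. The downside is that a single serious event judged only possibly related would hold patient dosing until the existing DSC decides, and the documents set no time for that decision. That is the standard already set for volunteers.
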